7.4.2 Benefit assessment

There is no direct benefit for study subjects from participation in the trial. It will be made clear that the vaccine is experimental and is not protective against malaria. Subjects may indirectly benefit from general medical evaluation and health screening procedures including testing for HIV, hepatitis B, and hepatitis C. Subject will be informed about the results of the screening and if necessary, they will be referred to their primary physician where they will receive counselling and further medical attention earlier than if they did not know of their disease status. Subjects will receive a financial compensation which is reasonable and in line with Dutch common practice (see below).

7.5 Description and justification of route of administration and dosage

Enrolled participants will receive four intra-muscular injections of the vaccine in the deltoid muscle, on alternating sides. The administration site minimizes the risk that the product is injected into a blood vessel. In case of suspicion that a blood vessel is hit, the vaccine will not be administered. In case of trauma or anatomical abnormalities the same arm may be used for subsequent injections.

Each volunteer will receive four equal doses of the vaccine on days 0, 28, 56, and 168. The trial is designed to evaluate the safety and tolerability in with a staggered dose escalation step of two dosages (30 µg and 100 µg). The interval of 4 weeks between immunizations 1, 2 and 3 is the most commonly used interval between malaria vaccine administrations, but in this trial also chosen to align with the RTS,S vaccination scheme. An additional fourth vaccination is given on day 168 as a booster, as promising effects of this fourth, delayed dose were seen in a trial with the Pfs25 transmission blocking vaccine candidate[19]. The low dose in this protocol is based on pre-clinical data (see above), and similar to starting concentrations in other malaria protein vaccine trials[20, 21].

7.6 Dose preparation and administration

Dose preparation, as described in the Pharmacy Manual, will be carried out by qualified personnel. The investigational product will be administered by intramuscular injection in the deltoid muscle in 2 different doses, 30µg R0.6C for groups 1 and 2, and 100µg R0.6C for groups 3 and 4. R0.6C is formulated pre-adsorbed to Alhydrogel (100ug R0.6C per 500uL of

[200 μ g R0.6C/mL, 1.6 mg Al(OH)₃/mL). Each vial contains 0.8 mL vaccine. Matrix-M is formulated as 750 μ L per vial at a concentration of 375 μ g/mL.

In groups A, a volume of 150 μ L of R0.6C/Alhydrogel will be aspired from the vial for the dose of 30 μ g R0.6C (groups 1A+2A) and a volume of 500 μ L will be aspired for the dose of 100 μ g R0.6C (groups 3A+4A).

For groups B a volume of 210 μ L Matrix-M will be added to each vial containing 800 μ L of R0.6C/Alhydrogel and mixed repeatedly by inversion by hand 10 times. Then 190 μ L of R0.6C/Alhydrogel + Matrix-M formulation will be aspired for administration of the 30 μ g dose (groups 1B+2B). For the 100 μ g dose groups (groups 3B+4B) 630 μ L of R0.6C/Alhydrogel + Matrix-M formulation will be aspired for administration. Receipt and disposal of the investigational products will be done according to RUMC SOPs. All vials containing the study product R0.6C/Alhydrogel and Matrix-M, will be stored at 2-8°C, and storage temperatures will be monitored with validated temperature monitoring devices.

7.7 Preparation and labelling of Investigational Medicinal Product

Preparation and labelling of the investigational medicinal products will be done according to the relevant GMP guidelines. After the products are QP-released there will be no manufacturing steps. Dose preparation is described in the Pharmacy Manual.

7.8 Drug accountability

The drug product and adjuvants will be shipped to Radboudumc according to the relevant national and international regulations. The site pharmacist will maintain complete records of all study products received from the sponsor and an accurate record of the inventory, and an accountability record of R0.6C supplies for this study. The site pharmacist will also ensure the security of these documents. Partially used vials will not be used for human administration or for in vitro experimental studies. Unused or open products will be either returned to the sponsor or designee at the end of the vaccination period or destroyed according to the sponsor's instructions.

8. METHODS

8.1 Study endpoints

Primary safety Endpoints:

- 1) The number of serious adverse events and solicited and unsolicited grade 3 adverse events possibly, probably or definitely related to the vaccine in the period from first R0.6C administration up to 84 days after the last immunization.

Primary efficacy endpoints:

- 1) The functional transmission reducing activity in the standard membrane feeding assay of volunteer sera collected two weeks after the fourth R0.6C immunization (I4+14), compared to baseline (I1-1) within each of the four dose-adjuvant groups.

Secondary safety endpoints:

- 1) The number of solicited and unsolicited grade 1 and 2 adverse events possibly, probably or definitely related to the vaccine in the period from first R0.6C administration up to 84 days after the last immunization.

Secondary efficacy endpoints:

- 1) The TRA at other timepoints (I1+14, I2+14, I3+14, I3+111 [I4-1], and I4+84) compared to baseline (I1-1) in each of the four dose-adjuvant groups.
- 2) The anti-6C antibody quantity in volunteer sera collected two weeks after fourth R0.6C immunization (I4+14) and at other time points (I1+14, I2+14, I3+14, I3+111 [I4-1], and I4+84) compared to baseline (I1-1) in each of the four dose-adjuvant combinations, as determined by ELISA.

Exploratory Endpoints:

- 1) The functional TBA in the SMFA of volunteer sera collected at different time points compared to baseline (I1-1) in each of the four dose-adjuvant combinations.
- 2) The anti-6C antibody decay rate following R0.6C immunization for each of the four dose-adjuvant combinations.
- 3) The anti R0.6C and anti-R0 antibody quantity in volunteer sera collected at different time points in each of the four dose-adjuvant combinations.
- 4) The cellular immune responses in volunteers samples collected at different time points in each of the four dose-adjuvant combinations.
- 5) The difference in TRA between the two dose groups (30 or 100 μ g R0.6C) and/or between adjuvant groups (alhydrogel and alhydrogel+Matrix-M).
- 6) The difference in peak anti-6C antibody quantity between the two dose groups (30 or 100 μ g R0.6C) and/or between adjuvant groups (alhydrogel and alhydrogel+Matrix-M).

8.2 Randomisation, blinding and treatment allocation

This will be an open-label trial to enable appropriate safety evaluation prior to proceeding to the next dose group. Subjects may choose in which of the dose groups (group 1-4) they wish to be enrolled. The time of notification and treatment group will be documented in the electronic case report form (eCRF).

Randomization will be used only for the allocation to one of the two different adjuvant combinations (arms A or B). The volunteers will be allocated to one of the two adjuvant arms per group at random using a Mersenne-Twister random number generator implemented in R. Randomization tables and randomization cards will be generated using the package "blockrand". Stratification will not be performed. An independent investigator at the Radboudumc, not involved in the clinical trial, is responsible for performing the randomization and for assigning volunteers according to the randomization cards. A second employee, not

involved in the assignment of volunteers, will check to see if randomization is done correctly. The randomization cards are kept in a fireproof clinical trial cabinet at Radboudumc.

8.3 Study procedures

8.3.1 Screening visit

The screening appointment for individual subjects is planned at least 72 hours after the subject has received the information sheet and the informed consent form. The purpose of the screening visit is to provide and clarify study information to the volunteer and to answer any questions the subjects may have, prior to obtaining informed consent and determining whether interested subjects are eligible for participation. The trial physician is responsible for providing the study information and performing the medical screening. A study nurse may draw venous blood, and measure vital parameters.

Upon arrival for the screening visit, the volunteer is asked to fill out a medical questionnaire. Subsequently, and prior to any screening activities, study staff will review the informed consent process with the volunteer. The possibility of withdrawal from the study, at any time and without any declaration of the reason, will be pointed out to the subjects. The subject will be required to pass a (short) written quiz about the study in order to ensure the study subjects has sufficient understanding of what participation entails.

The investigator, or a person designated by the investigator, will fully inform the volunteer of all pertinent aspects of the study and individual consent will be documented by a signature. Subjects may only participate in screening if they have signed the informed consent form. All subjects must consent to an HIV, hepatitis B and hepatitis C serological screening, urine toxicology and for females also a pregnancy test. Subjects who sign the informed consent will undergo screening. If certain elements of the screening procedures already indicate that a subject is ineligible for inclusion, screening procedures do not necessarily all have to be completed. The below activities will occur during the screening:

- Patient history: the answers to the medical questionnaire are discussed with the volunteer and clarified where needed. The subject will be further interviewed to collect demographic data, medical history including details of any chronic or recurrent medical and psychiatric conditions and use of adequate contraception;
- Study information: the study schedule and study rules are discussed with the subject and any questions are answered;
- A physical examination including vital signs, height and weight will be performed;
- Blood specimens will be collected for routine clinical laboratory testing of biochemical and hematological parameters, as well as HIV, hepatitis B and hepatitis C serological screening;
- A urine specimen will be collected for toxicology screening and for females a pregnancy test if the subject is of childbearing potential;
- Consent to inform the general practitioner (and if necessary a medical specialist) of study participation and request relevant information on medical history, will be signed

by the subject and sent after screening.

If physical examination, vital signs or laboratory values are out of the normal range, a repeat measure may be obtained as deemed necessary by the investigators. The medical history, physical examination, and laboratory findings for subjects will be recorded in the source screening data documents. All subjects will be asked to supply a phone number of a partner or roommate who may be contacted in case of emergency. Concomitant medications is recorded at all study visits.

All results of the screening will be reviewed with the subject. Subjects are informed in person or by phone if they have satisfied all the inclusion criteria. If clinically significant abnormalities are identified during screening, subjects will be referred to their primary health provider or appropriate medical center. If identified during the study, subjects may be asked to return to the study site for further evaluation, including clinical evaluation and repeat laboratory testing as warranted.

8.3.2 Medical history

The trial clinician will review the medical history of potential study subjects during the screening visit. The starting point will be a medical questionnaire the subjects have filled in before the screening. Particular attention will be paid to:

- Current or recent (within the previous two weeks) acute respiratory illness with or without fever, including symptoms associated with COVID-19;
- Recent receipt of vaccinations or other immune modulator therapy within the previous six months;
- Hypersensitivity of any kind;
- Clinically relevant history of cardiovascular, renal, gastrointestinal, hematological, dermatological, endocrine, neurological or immunological diseases;
- Known or suspected immunologic function impairment of any kind and/or known HIV infection, hepatitis B or hepatitis C infection;
- Mental illness;
- Tobacco, alcohol, or drug use;
- Medication use in the past 6 months;
- For women, pregnancy and contraceptive use and/or history of surgical sterility.

8.3.3 Physical examination

A complete physical examination will include the examination of general appearance, skin, neck, eyes, throat, lungs, heart, abdomen, back and extremities, and a routine vascular and neurological examination. Height (cm) and body weight (to the nearest 0.1 kilogram [kg] in indoor clothing, but without shoes) will also be measured, at screening only. Body mass index (BMI) will be calculated using the formula: $BMI = \text{Body weight (kg)} / [\text{Height (m)}]^2$ and converted to an integer. During follow-up visits a focused physical examination will be performed if deemed necessary by the trial physician.

8.3.4 Vital signs

Vital signs including body temperature (degrees Celsius), blood pressure (BP, millimeters of mercury) and pulse measurements (beats per minute) will be recorded at the screening and inclusion visit. Additional measurements will take place at the discretion of the physician. Systolic and diastolic BP will be measured while the subject is sitting, with back supported and both feet placed on the floor, using an automated validated device, with an appropriately sized cuff. In case the cuff sizes available are not large enough for the subject's arm circumference, or in case of doubt of accuracy of the automated device a sphygmomanometer with an appropriately sized cuff may be used. If vital signs are out-of-range at screening or inclusion, the investigator may obtain two additional readings, so that a total of up to three consecutive assessments are made, with the subject seated quietly for approximately five minutes preceding each repeat assessment. At least the last reading must be within the normal range in order for the subject to qualify. Temperature, blood pressure and pulse are measured as part of the physical examination at screening and inclusion. Additionally, subjects will be given a thermometer to measure their oral temperature on a daily basis for two weeks after each R0.6C administration, which they will collect in their study diaries.

8.3.5 Inclusion visit

Subjects meeting the eligibility criteria during screening (section 5.2 and 5.3) will be invited back for enrolment into the study at the inclusion visit, which will occur prior to the planned first administration. Baseline assessments will be taken on the inclusion day. For each subject, study start (day 0) will be defined as the day of first R0.6C administration. For subjects that do not show up for the inclusion visit, or subjects that do not continue to meet the eligibility criteria, alternate subjects may take their place. At study inclusion, the following activities will occur:

- Patient history will be repeated. Only subjects who still meet the inclusion criteria will be included to receive R0.6C vaccination;
- Blood specimens will be collected for routine clinical laboratory testing of biochemical and hematological parameters;
- A urine specimen will be collected for toxicology screening and for females a pregnancy test if the subject is of childbearing potential;
- Subject will be issued symptom diaries and a thermometer to record any local and systemic symptoms and medication use;
- All subjects will be issued an emergency notification card that details their participation in the study and provides contact phone numbers of the investigators.

8.3.6 Administration of R0.6C TBV candidate

Each enrolled subject will receive a total of four R0.6C vaccinations. The first vaccination will take place on day 0, the second on day 28 (+/- 3 days), the third on day 56 (+/- 3 days) and the last vaccination on day 168 (+/- 7 days). Subjects will be briefly assessed regarding any new medical events since the inclusion visit. The R0.6C vaccination will be prepared at bedside by study staff (nurse, study physician) or by the pharmacy according to the study arm; arms A will receive R0.6C with Alhydrogel alone, arms B will receive R0.6C with Alhydrogel and Matrix-M. R0.6C will be administered intramuscular in the deltoid muscle on alternating sides. The site of injection will be recorded on the case report form. Subjects will be observed for at least 1 hour after R0.6C administration. A list of solicited local and systemic symptoms will be reviewed after this observation period. If the occurrence of an adverse event or use of medication is confirmed by the study physician, it is recorded in the eCRF. After leaving the hospital, subjects will be asked to examine the site of infusion and record local signs and symptoms for seven days including bruising, erythema, swelling or induration. Subjects will be asked to record any AEs in the memory aid booklet (also see section 8.3.9).

8.3.7 Follow up after R0.6C administration

Follow-up visits will be carried out on an outpatient basis at the study center. Subject will be asked to record local signs and symptoms in their memory aid booklet (also see section 8.3.9). The subject diary will be reviewed at each study visit and used as a base for discussion of possible local and systemic adverse events or medication use. In such cases, it may not be possible to obtain blood samples for non-safety endpoints.

If clinically significant (laboratory) abnormalities are identified during the study, subjects may be asked to return to the study site for further evaluation, including clinical evaluation and repeat laboratory testing as warranted. The trial physician can decide to initiate any additional diagnostics (including safety laboratory evaluations) at all times. For unexpected laboratory abnormalities, the laboratory test will be repeated.

8.3.8 Unscheduled visits

Subjects may need to present to the study center during operating hours for an unscheduled visit should they experience any AE that requires evaluation by the trial clinician. Data for any examinations performed on the subject at an unscheduled visit must be recorded in the eCRF. If an unscheduled visit is performed, the procedures for the next following visit should not be made earlier than scheduled above.

8.3.9 Patient reported outcomes (study diary)

At the inclusion visit, subjects will be issued symptom diaries. They will be asked to record all symptoms and medication use from the day of inclusion until end of study. Study staff will train subjects on use of memory aid booklets for self-assessment of solicited local and general adverse events through 7 days (day of R0.6C administration and subsequent 6 days) post- administration of R0.6C; and for self-assessment of adverse events and concomitant medications until day 84 after the last R0.6C administration.

The subject diary will be reviewed at each study visit and used as a basis for discussion of possible adverse events or medication use. If the occurrence of an adverse event or use of medication is confirmed by the study physician, it is recorded in the subject's EPD and eCRF. At the end of the study, the diary will be collected and kept as source data.

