9.2 AEs, SAEs and SUSARs

9.2.1 Adverse events (AEs)

Adverse events are defined as any undesirable experience occurring to a subject during the study, whether or not considered related to the investigational product. All adverse events reported spontaneously by the subject or observed by the investigator or his staff will be recorded. Abnormal laboratory findings (e.g. clinical chemistry or hematology) or other abnormal assessments that are judged by the investigator to be clinically significant will be recorded as AEs (or SAEs if they meet the definition). The investigator will exercise his or her medical and scientific judgment in deciding whether an abnormal laboratory finding or any other abnormal assessment is clinically significant. If there are any severe complaints, the volunteer will be evaluated immediately by a qualified clinician using the appropriate clinical assessments according to standard hospital care.

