9.2.2 Adverse event data collection and recording

Adverse events will be collected at all follow-up visits, using the memory aid booklets as a basis (see section 8.3.9), and whenever a subject reports signs or symptoms to the trial physician between visits.

After administration with R0.6C the following systemic signs and symptoms will be solicited until 14 days after administration:

Fever, headache, myalgia, fatigue, chills, and rash. The time points that these symptoms are solicited are indicated in section 8.3.17.

After the administration of R0.6C the following local signs and symptoms will be solicited until 7 days after administration:

Pain, itching, swelling, induration and redness at injection site. The time points that these symptoms are solicited are indicated in section 8.3.17.

If known, the trial clinician will record the diagnosis (i.e., disease or syndrome) rather than component signs, symptoms and laboratory values. If the signs and symptoms are considered unrelated to an encountered syndrome or disease they should be recorded as individual AEs. If a primary AE is recorded, events occurring secondary to the primary event should be described in the narrative description of the case (e.g. primary AE = Orthostatic hypotension; secondary event may be fainting, head trauma, etc.). In case of hospitalizations for surgical or diagnostic procedures, the pre-existing condition should be recorded as the SAE, not the procedure itself.

All adverse events/reactions (solicited and unsolicited) will be accurately documented in the case report form by the investigators. For each event/reaction the following details will be recorded:

1. Description of the event/reactions (ICD-10 terminology will be included in the eCRF)
2. Duration (date and time of occurrence and end date and time)
3. Intensity (see explanation directly below)
4. Relationship with the intervention (see section 9.2.3)
5. Action taken, including treatment

The intensity of the symptoms will be ranked as (1) mild, (2) moderate, (3) or severe, according to the following scale:

Mild (grade 1):	awareness of symptoms that are easily tolerated and do not interfere with usual daily activity
Moderate (grade 2):	discomfort that interferes with or limits usual daily activity
Severe (grade 3):	disabling, with subsequent inability to perform usual daily activity, resulting in absence or required bed rest

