9.2.5 Suspected unexpected serious adverse reactions (SUSARs)

Adverse reactions are all untoward and unintended responses to an investigational product related to any dose administered. Unexpected adverse reactions are SUSARs if the following three conditions are met:

1. the event must be serious (see section 9.2.4);
2. there must be a certain degree of probability that the event is a harmful and an undesirable reaction to the medicinal product under investigation, regardless of the administered dose;
3. the adverse reaction must be unexpected, that is to say, the nature and severity of the adverse reaction are not in agreement with the product information as recorded in:
 - Summary of Product Characteristics (SPC) for an authorised medicinal product;
 - Investigator's Brochure for an unauthorised medicinal product.

The sponsor will report expedited the following SUSARs through the web portal *ToetsingOnline* to the METC:

- SUSARs that have arisen in the clinical trial that was assessed by the METC;
- SUSARs that have arisen in other clinical trials of the same sponsor and with the same medicinal product, and that could have consequences for the safety of the subjects involved in the clinical trial that was assessed by the METC.

The remaining SUSARs are recorded in an overview list (line-listing) that will be submitted once every half year to the METC. This line-listing provides an overview of all SUSARs from the study medicine, accompanied by a brief report highlighting the main points of concern. The expedited reporting of SUSARs through the web portal Eudravigilance or *ToetsingOnline* is sufficient as notification to the competent authority. The sponsor will report expedited all SUSARs to the competent authorities in other Member States, according to the requirements of the Member States. The expedited reporting will occur not later than 15 days after the sponsor has first knowledge of the adverse reactions. For fatal or life threatening cases the term will be maximal 7 days for a preliminary report with another 8 days for completion of the report. As this is an open label study in which the sponsor, investigator and the SMC are not blinded, the code would not have to be broken in the case of a SUSAR.

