10.1 Primary study parameter(s)

The number of subjects enrolled, completed, or withdrawn will be summarized. Reasons for withdrawal, when known, will be provided. Demographic data will be summarized by descriptive statistics and will include total number of observations (n), mean, standard deviation (SD) and range for continuous variables, and number and percentages for dichotomous variables. The primary safety, and reactogenicity outcomes will include all subjects who meet the eligibility criteria, received the study product R0.6C, and for whom safety data are available.

Safety endpoints

For the safety analysis, data from all subjects who received at least one dose of R0.6C and for whom safety data are available will be included. All analyses will be descriptive. Data will be presented by dose, overall/dose and overall/subject. Results will be summarized by study group. The percentage of subjects with at least one local AE (solicited or unsolicited), with at least one general AE (solicited or unsolicited) and with any AE during the solicited follow-up period will be tabulated with exact 95% CI (two-sided). No multiplicity adjustment will be implemented in analysis. The same calculations will be performed for AEs rated as grade 3.

The percentage of subjects reporting each individual solicited local and general AE during the solicited follow-up period will be tabulated with exact 95% CI. The same tabulation will be performed for grade 3 AEs and for AEs with relationship to R0.6C administration. The reports of unsolicited AEs will be reviewed by a physician and will be categorized by ICD-10. The percentage of subjects with at least one report of unsolicited AE and reported up to 28 days after R0.6C administration will be tabulated with exact 95% CI. The same tabulation will be performed for grade 3 unsolicited AEs and for unsolicited AEs with a relationship to R0.6C administration. SAEs will be described in detail. Withdrawals due to AEs/SAEs will also be summarized. Vital signs which are outside of the normal range and clinically significant will also be listed in tables. The frequency of signs and symptoms will be compared between groups with the chi-square test or fishers exact test. Serious adverse events (SAEs) occurring at any point during the trial will be summarized and relatedness to vaccine will be assessed.

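### The confirmation step for diary symptoms and the rule preferring a diagnosis to its symptoms are inconsistent with the solicited-symptom tables they feed

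*Protocol*

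**What the plan says.** Four sets of statements bear on how a solicited symptom reaches the analysis.

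- **Confirmation.** Protocol 8.3.9 makes the diary the starting point for discussion at each visit and continues: "If the occurrence of an adverse event or use of medication is confirmed by the study physician, it is recorded". Protocol 8.3.6 says the same of events found when the solicited list is reviewed after the observation hour: an event that "is confirmed by the study physician, it is recorded in the eCRF". Neither section says what confirming consists of. Protocol 9.2.5 describes the blinding: "As this is an open label study in which the sponsor, investigator and the SMC are not blinded".
- **Complete recording.** Protocol 9.2.1: "All adverse events reported spontaneously by the subject or observed by the investigator or his staff will be recorded". Protocol 9.2.2: "All adverse events/reactions (solicited and unsolicited) will be accurately documented in the case report form by the investigators". Neither sentence mentions confirmation.
- **Diagnosis before symptoms.** Protocol 9.2.2: "If known, the trial clinician will record the diagnosis (i.e., disease or syndrome) rather than component signs, symptoms and laboratory values". The next sentence limits this: "If the signs and symptoms are considered unrelated to an encountered syndrome or disease they should be recorded as individual AEs". The solicited list in the same section has six systemic symptoms (fever, headache, myalgia, fatigue, chills, rash) and five local ones. It is not exempted from the diagnosis rule.
- **Tables.** Protocol 10.1: "The percentage of subjects reporting each individual solicited local and general AE during the solicited follow-up period will be tabulated with exact 95% CI". SAP Table 1 gives each solicited event type its own rows by grade, with subject counts and percentages per dose-adjuvant group, restricted to events assessed as related. The SAP describes unsolicited events by number of events under ICD-10 categories.

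**The concern.** The per-symptom tables are meant to show how many subjects reported each reaction. Headache, fatigue, myalgia, chills and injection-site pain are known mainly from the subject's own account. If entry follows confirmation by a physician who knows the dose and adjuvant, with no stated criterion, two members of staff can treat the same diary entry differently and each can cite the protocol.

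The diagnosis rule raises a separate problem. Several of the solicited systemic symptoms could be summarised together as one syndrome. Followed as written, the rule puts the syndrome in the eCRF in place of the symptoms that the tables are built to count.

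This matters because the protocol's sample size section describes the study as intended mainly to provide safety data. Summaries of solicited events by severity also go into the safety reports for the safety monitoring committee (9.5.3), which reviews these data before each group progression (9.5.4).

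**Working it through.** The point concerns recording rules, so most of the check sets the sections side by side. The plan states no capture or confirmation rate. Its one quantified safety statement, in the SAP sample size section, is a 7% event rate detectable with 90% probability in 32 participants. That reproduces: 1 − (1 − 0.07)^32 = 0.902. It concerns seeing at least one clinically significant event, and this point does not change it.

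1. **Confirmation against complete recording.** Sections 8.3.6 and 8.3.9 attach a condition to eCRF entry; 9.2.1 and 9.2.2 attach none; 10.1 counts what subjects report. No section says which governs an entry the physician does not confirm, and none says the tables are built directly from the diaries.

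2. **Diagnosis rule against the tables.** The rule operates when a diagnosis is known and the symptom is attributed to it. Take a subject with fever, chills, myalgia, headache and fatigue, recorded as one syndrome:
   - Under the diagnosis rule, the eCRF holds one entry and none of the five component symptoms.
   - Under 10.1 and SAP Table 1, the subject is then absent from five per-symptom rows.
   - The syndrome is not on the solicited list, so it would naturally fall under unsolicited events. There the SAP counts events rather than subjects.
   - The sentence that all solicited events are documented does not settle this, because the syndrome itself can be read as the documented event.

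3. **Which tables are affected.**
   - *Syndrome assessed as related:* the five symptoms can be missing from both SAP Table 1 and the protocol 10.1 table.
   - *Diagnosis assessed as unrelated:* SAP Table 1 would leave the symptoms out in any case. The loss falls on the 10.1 table, which covers solicited events whatever their cause.
   - *Local symptoms:* injection-site reactions are hardly touched, as they are rarely components of a systemic syndrome.

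4. **Effect on Endpoint 1.** A related grade 3 syndrome still counts, because the endpoint includes unsolicited as well as solicited grade 3 events. It counts as one event, where five grade 3 symptoms recorded separately would count as five.

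5. **Size of one omission.** Each dose-adjuvant group has 8 subjects, so one subject missing from a row moves it by 1/8 = 12.5 percentage points. The exact 95% limits for x of n are the 0.025 quantile of Beta(x, n − x + 1) and the 0.975 quantile of Beta(x + 1, n − x):
   - 3/8 = 37.5%, interval 8.5% to 75.5%
   - 2/8 = 25.0%, interval 3.2% to 65.1%

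   The starting value of 3/8 is an illustration, not a prediction.

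**The case against.** The strongest reply is that the sections, read together, already presuppose individual recording. Section 9.2.2 names solicited events when it says everything is documented, lists the symptoms one by one, and keeps symptoms not tied to a syndrome as separate events. Section 10.1 and SAP Table 1 then give each symptom its own row. Nothing says that vaccine reactogenicity will be coded as a syndrome. Diaries are kept as source data, and 12.2 has the recording of primary and safety variables checked in at least 50% of subjects.

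Much of this stands, and it rules out some stronger readings.

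- **A reader might infer that a diary symptom reaches the eCRF only if confirmed.** The text does not say so. It says what happens on confirmation, and 9.2.1 and 9.2.2 promise complete recording. The protocol is inconsistent; it does not establish a filter.
- **A reader might treat days without a visit as days on which symptoms are lost.** Confirmation need not mean examination. It can be a conversation over the diary, which is reviewed at every visit, and 9.2.2 also collects events reported between visits. Visit spacing is not a measure of loss.
- **A reader might infer that the strongest reactors are the most likely to be recorded as a syndrome, or that recording will differ by arm.** Both are conceivable, but the documents give no evidence for either.

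What does not stand is that these points resolve the conflict. The diagnosis rule has no exemption for solicited symptoms, so staff who apply it literally are following the protocol. A source check would not clearly flag an omission that the protocol permits.

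**Conclusion.** The recording rules are inconsistent with the tables they feed, and the diagnosis rule, applied as written, can empty the per-symptom rows. This is worth correcting because the remedy is cheap and the tables are a main product of the trial.

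Loss is possible, not shown. The documents give no confirmation rate and no frequency of syndrome diagnoses, so its size cannot be computed; the only firm figure is 12.5 percentage points per missing subject in a group of 8. The effect falls mainly on systemic symptoms.

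The conclusion assumes that the tables are built from eCRF entries, since no section provides for tabulating the diaries directly.

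**What to change.** - **Protocol 8.3.6 and 8.3.9, reconciled with 9.2.1, 9.2.2 and 10.1:** enter every solicited symptom recorded within its window into the eCRF as reported, with its highest intensity. The physician adds causality and comments but cannot remove the record. Settle the window in the same edit: 8.3.9 trains diary self-assessment of solicited general events through 7 days, while 9.2.2 solicits systemic symptoms until 14 days. These must be reconciled.
- **Protocol 9.2.2:** limit the preference for a diagnosis over its component symptoms to unsolicited events. Where a diagnosis explains a solicited symptom, record it as an additional linked event, flagged so that event counts do not include both.

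The cost is protocol wording, eCRF completion guidance, more data entry and slightly higher reported reactogenicity. If data collection is already complete, the retained diaries still allow eCRF entries to be reconciled against them.

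The change protects the per-symptom tables. It does not remove the unblinded causality assessment that decides entry to Endpoints 1 and 3 and to SAP Table 1, nor does it blind the subjects who fill in the diaries.
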